3. OVERALL STUDY DESIGN AND PLAN

3.1 Study Design

This is a phase 2a, multicenter, open-label, dose-escalation study to evaluate the safety and efficacy of DAXI for injection for the treatment of subjects with moderate to severe LCL. This study will be conducted at 4 sites in the United States.

[figure not shown]
[REDACTED]

[figure not shown]
Approximately 64 subjects (18-65 years of age) with moderate to severe LCL will be enrolled [REDACTED]

[figure not shown]
[REDACTED] The total study duration will be up to 38 weeks including up to 2 weeks for screening. Subjects will be followed for a minimum of 24 weeks and up to 36 weeks or until scores on the IGA-LCWS and PLCWS return to baseline (Day 1 Visit) or until Week 36, whichever occurs first. Subjects will then have a Final Evaluation Visit. [REDACTED]

[REDACTED]

A Data Review Committee (DRC) will be used to review available data and will determine whether to proceed to the subsequent cohorts. Cohorts 1 and 2 will be enrolled simultaneously and the DRC will review data 4 weeks after LCL treatment for the last subject in Cohorts 1 and 2. The DRC will convene again after the last subject in Cohort 3 reaches the Week 4 visit.

Statistical Analysis Plan for 1820205

3.1.1 Determination of Sample Size

The sample size is not determined by the power of formal hypothesis tests.

3.1.2 Treatments Administered

This is an open-label, non-randomized study for the treatment of moderate or severe LCL. Subjects will be sequentially enrolled by cohort.

3.2 Efficacy and Safety Assessments

The primary effectiveness assessments will include investigator assessment of LCL severity and improvement, as well as subject assessment of severity and improvement on the IGA-LCWS and PLCWS, respectively.

3.2.1 Lateral Canthal Wrinkle Severity – Patient and Investigator Global Assessment

Lateral canthal wrinkle severity is assessed by both the subject (PLCWS) and the investigator (IGA-LCWS) using the same 4-point rating scale, where scores range from 0 = none to 3 = severe.

3.2.2 Global Aesthetic Improvement Scale

The Investigator and subject will assess the visual appearance (at maximum smile) of the improvement from the baseline condition in LCL using the 7-point severity GAIS. The scale ranges from -3 = Very much worse to 3 = Very much improved, with a rating of 0 = No change.

3.2.3 Facial Age Self Evaluation

At each clinic visit, the subject will be asked to rate their perceived age using the FASE questionnaire (see Appendix 7 of the protocol).

3.2.4 FACE-Q™

At each clinic visit, the subject will be asked to complete the FACE-Q™ Appraisal of Lines: Crow's Feet Lines questionnaire (see Appendix 9 of the protocol). The questionnaire asks subjects to rate how bothered they are by their LCL using 7 questions about general appearance with a rating scale of 1 to 4 with 1 = Not Bothered and 4 = Extremely Bothered.

[Redacted text block]

Statistical Analysis Plan for 1820205

3.2.7 Subject Global Satisfaction with Treatment Questionnaire

At each clinic visit after treatment, the subject will be asked to complete the Subject Global Satisfaction with Treatment Questionnaire to rate their satisfaction with the treatment results using a 7-point scale. The scale ranges from 0 = Very Dissatisfied to 6 = Very Satisfied, with a rating of 3 = Neither Satisfied nor Dissatisfied.

3.3 Safety Assessments

3.3.1 Adverse Events

All adverse events (AEs) will be recorded and classified on the basis of MedDRA terminology. AE severity will be graded as mild, moderate, or severe as defined in Section 8.5.7 of the protocol. Relationship of an AE will be graded as definite, probable, possible, or unrelated. AEs with an onset on or after the date and time of trial treatment or events which were present before treatment and which worsened after treatment will be considered as treatment-emergent.

AEs with missing severity will be considered as “severe”. AEs with missing relationship will be considered as “related”. If the start of an AE relative to the administration of trial treatment cannot be definitively determined, it will be considered to have occurred after treatment and the event considered as treatment-emergent.

[REDACTED]

3.3.3 Injection Site Evaluation

Injection sites will be evaluated at screening for signs of skin inflammation or active disease and at Day 1 (pre- and post-treatment), Week 2 and Week 4 visits. The assessment will be done as a global evaluation of the 3 injection sites for LCL on each side of the face. The presence of erythema, edema, burning or stinging, itching or bruising will be captured as medical history (pre-treatment) or as an AE (post-treatment).

3.3.4 Clinical Laboratory Data

3.3.4.1 Clinical Safety Laboratory Data

As outlined in [Table 3.3.4-1](#), non-fasting samples for hematology, chemistry, PT (screening only) and urinalysis will be collected at screening, the Week 4 Visit, and the Week 36 or Final Evaluation Visit. [REDACTED] Urinalysis will be evaluated at the study center.

Statistical Analysis Plan for 1820205

[figure not shown]
Table 3.3.4-1: Clinical Laboratory Tests

Serum Chemistry	Hematology	Urinalysis	Additional Tests
Glucose	Hemoglobin	Specific gravity	Prothrombin time (PT; screening only)
Total bilirubin	Hematocrit	pH	
Alanine aminotransferase	Leukocyte Count (total)	Glucose Protein	UPT (WOCBP only)*
Aspartate aminotransferase	Leukocyte Count (differential)	Blood Bilirubin	
Alkaline phosphatase	Red Blood Cell Count	Ketones	
Blood urea nitrogen	Platelet Count		

WOCBP = Women of child-bearing potential

3.3.4.2 Pregnancy Test

Urine pregnancy tests (UPT) will be performed at screening, baseline (prior to treatment) and at the Week 36 or Final Evaluation Visit. A serum pregnancy test will be performed to confirm pregnancy whenever a post-treatment UPT is positive.

Statistical Analysis Plan for 1820205

3.3.5 Vital Signs

Vital signs (i.e., body temperature, respiration rate, sitting radial pulse rate, and sitting systolic and diastolic blood pressures) will be obtained at the screening, Day 1, Week 2, and Week 36 or Final Evaluation Visits, [REDACTED]. New abnormal findings or worsening from baseline (Day 1 prior to LCL treatment) at subsequent assessments, if judged clinically significant, should be recorded as an AE.

3.3.6 Physical Examination

A targeted physical examination, [REDACTED] will be conducted at screening, Day 1, Week 2 and Final Evaluation Visits. Significant physical examination findings that are present prior to investigational product administration will be reported as Medical History.

Significant physical examination findings after investigational product administration which meet the definition of an AE will be recorded as an AE.

[REDACTED]

[REDACTED]

3.4 Interim Analyses and Data Monitoring**3.4.1 Data Review Committee**

Due to the dose-escalation nature of the study design, safety data and subject photographs/videos will be evaluated by the DRC at Week 4 following LCL treatment in Cohorts 1 and 2 (enrolled simultaneously) before a decision is made to move forward with the next and subsequent doses. The DRC will reconvene again after the last subject in Cohort 3 reaches the Week 4 Visit. Safety data will be monitored throughout the study by the DRC at regular intervals.

Dose escalation for LCL may be stopped at the discretion of the DRC as outlined in the DRC Charter. The full details for the roles and responsibilities of the DRC will be detailed in the study-specific DRC charter.

3.4.2 Interim Analysis

A formal interim analysis of the data will be performed when all subjects finish 8 weeks after receiving the LCL treatment or have withdrawn from the study earlier. This interim analysis will be a high level analysis of study conduct, efficacy and safety. The analysis will be performed by the study team in a restricted access folder. Efficacy will focus on the primary and secondary endpoints.

Individual tables, listings, and figures to be included in the interim analyses are denoted in [Section 9](#) below with an asterisk.

Statistical Analysis Plan for 1820205

4. ANALYSIS POPULATIONS AND SUMMARY GROUPS

Three analysis populations will be specified, ignoring cohort membership. These populations are: Enrolled, LCL-Evaluable, and Safety. Analyses performed will be based on the actual dose for LCL received (which is expected to be consistent with the enrollment cohort).

4.1 Enrolled Population

All subjects who receive the LCL treatment. A subject will be considered “enrolled” if they receive any investigational product including a partial dose.

4.2 LCL-Evaluable Population

All enrolled subjects who receive the LCL treatment and have any post-LCL treatment assessment of IGA-LCWS at maximum smile.

4.3 Safety Population

All enrolled subjects.

[REDACTED]

5. CONVENTIONS AND DERIVATIONS

5.1 Definition of Baseline

The baseline value will be the last available non-missing value prior to LCL treatment on Day 1. Assessments taken on the same day as LCL treatment will be assumed to be prior to treatment unless indicated to be obtained post-treatment.

5.2 Definition of Day 1

Day 1 of LCL treatment is defined as the day of DAXI dose for LCL treatment. All time-to-event analyses for assessments of LCL will utilize the date of LCL treatment as the start date.

5.3 Demographic and Disposition

Age in years at time of enrollment will be derived relative to the date of informed consent as (consent date – date of birth + 1)/365.25 and truncated to 0 decimal points. Age will also be categorized into two groups: <65 years and ≥65 years.

[REDACTED]

Statistical Analysis Plan for 1820205

AEs with missing severity will be summarized as “severe”. AEs with missing relationship will be summarized as “related”.

6. STATISTICAL METHODS

All statistical programming will be performed using statistical analysis system (SAS) version 9.4 or higher.

6.1 Subject Disposition

The number and percentage of subjects who have signed informed consent, enrolled, received treatment, and completed visits will be tabulated by summary cohort and overall; and, included in a listing. Reasons for not completing the study will also be tabulated by summary cohort and overall using numbers and percentages; this data will also be included in a listing. For those subjects who are considered to have failed screening, the reason(s) for failure will be provided in a listing.

The number and percentage of subjects included and excluded from the analysis populations will be tabulated overall and for each summary cohort. Reason(s) for exclusion from each population will be summarized and listed.

A summary of the duration of the subject participation in the study will be produced, including the n, mean, standard deviation (SD), median, first and third quartiles, minimum, and maximum duration in weeks, as well as the number and percentage of subjects in the duration categories.

Major protocol deviations will be listed and summarized by summary group.

6.2 Demographic and Baseline Characteristics

Descriptive statistics will be used to summarize demographic and baseline characteristics by summary cohort and overall.

Demographic data include age, age category, sex, ethnicity, and race. Baseline characteristics include prior Botulinum toxin Type A, time since last prior Botulinum toxin Type A injection, and Fitzpatrick skin type, as well as the baseline values of the efficacy assessments, PLCWS and IGA-LCWS. Summaries will be produced for the Enrolled population. If the LCL Evaluable or Safety population differs from the Enrolled population, then the summaries will be produced for the population(s) which differ from the Enrolled population.

6.3 Medical History

Medical history will be classified on the basis of MedDRA terminology, using the latest terminology at the time of database finalization. Medical history will be summarized for the Safety population by summary cohort and overall, by system organ class, and by preferred term; and, will be listed.

6.4 Prior and Concomitant Medications

Prior therapies/medications and concomitant therapies/medications will be coded using the World Health Organization (WHO) drug dictionary and summarized by Anatomical Therapeutic Chemical (ATC) second level term and Preferred Name for the Safety population. Prior and concomitant medications will be summarized separately.

Statistical Analysis Plan for 1820205

6.5 Efficacy Analyses

Descriptive statistics will be provided for all efficacy variables at all visits by cohort. A 95% exact CI will be provided for proportions. All analyses displaying proportions will use population counts as denominators at all visits regardless of the number of actual observations recorded. Differences between cohorts will not be presented except where specifically identified in the shells.

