4. STUDY DESIGN

4.1. Overall Design

This is a phase 2a, multicenter, open-label, dose-escalation study to evaluate the safety and efficacy of DAXI for injection for the treatment of subjects with moderate or severe LCL. This study will be conducted at 4 sites in the United States.

[REDACTED] Subjects will be screened for eligibility and enrolled into the study after providing informed consent.

Approximately 64 subjects (18-65 years old) with moderate or severe LCL will be enrolled sequentially into 1 of 4 treatment cohorts (approximately 16 subjects per cohort) [REDACTED]. Investigators will make all reasonable efforts to enroll equal proportions of patients with moderate and severe LCL (based on baseline assessments) in each dosing cohort. The total study duration will be up to 38 weeks, including up to 2 weeks for screening. Subjects will be followed for a minimum of 24 weeks and up to 36 weeks or until scores on the maximal expression IGA-LCWS and PLCWS return to baseline (Day 1 Visit), or until Week 36, whichever occurs first. Subjects will then have the Final Evaluation Visit.

Cohorts 1 and 2 will be enrolled simultaneously. Subsequent cohorts (3 and 4) will be enrolled sequentially and gated by the decision from the Data Review Committee (DRC) upon reviewing available data (including safety, efficacy, and photographs/videos) of previous cohorts. The DRC will convene to review data 4 weeks after LCL treatment for the last subject in Cohorts 1 and 2. The DRC will reconvene again after the last subject in Cohort 3 reaches the Week 4 Visit. Revance reserves the right to terminate or stop the study at any time. Refer to Sections 1.2 and 9.5.1 for additional information.

[REDACTED]

[REDACTED]	[REDACTED]	[REDACTED]

[REDACTED]

All treatments will be IM injections administered by the PI. [REDACTED]
[REDACTED]
[REDACTED]
[REDACTED]

The area around the injection sites will be evaluated at the Screening Visit to assess for skin inflammation or active skin disease and at the Day 1, Week 2, and Week 4 Visits to determine if there is a cutaneous reaction to the investigational product. The assessment will be captured as a

global evaluation of the injection sites to assess for erythema, edema, burning or stinging sensation, itching, or bruising.

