9.5. Interim Analyses

A formal interim analysis of the data will be performed 8 weeks after the last LCL treatment.

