6.6 Safety Analyses

Safety summaries and analyses will be performed on the Safety population and will be presented by cohort and in total across cohorts. Descriptive statistics will be presented to summarize the safety data. By visit safety summaries will use denominators based on the number of subjects with valid observations at that visit unless otherwise specified.

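### At the interim, the fixed population denominator would count subjects not yet due as non-responders at any visit after Week 8, mainly in Cohort 4

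*SAP*

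**What the plan says.** SAP 6.5 asks for by-visit results without a time limit, "Descriptive statistics will be provided for all efficacy variables at all visits by cohort", and then fixes the denominator: "All analyses displaying proportions will use population counts as denominators at all visits regardless of the number of actual observations recorded". It does not separate a visit that was missed from one that has not come due. Under SAP 4.2 a single post-treatment IGA-LCWS at maximum smile places a subject in the LCL-Evaluable population, so a subject only 8 weeks into follow-up is already in the denominator for every later visit.

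The interim trigger in SAP 3.4.2 is "A formal interim analysis of the data will be performed when all subjects finish 8 weeks after receiving the LCL treatment", or when they have withdrawn earlier. Protocol 9.5 has the same timing: "A formal interim analysis of the data will be performed 8 weeks after the last LCL treatment". On content, SAP 3.4.2 says "Efficacy will focus on the primary and secondary endpoints" and refers to asterisked items in SAP Section 9. Neither that list nor the secondary endpoints can be read in the public version.

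Protocol 4.1 enrols Cohorts 1 and 2 together. Cohort 3 waits for a Data Review Committee (DRC) review 4 weeks after the last Cohort 1 or 2 treatment, and Cohort 4 waits for a review after the last Cohort 3 subject reaches Week 4.

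**The concern.** A subject whose Week 12 visit lies after the data cut cannot be a Week 12 responder, yet the written rule keeps that subject in the Week 12 denominator. This is neither dropout nor exit after return to baseline; the data do not exist yet. Because enrolment is staged by cohort, the shortfall is not spread evenly. It falls first and hardest on the cohort treated last.

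In a dose-escalation study the cohort treated last is presumably the highest dose, although the doses are redacted. A by-visit interim table could therefore suggest that the effect wears off sooner at the top of the dose range when it does not. Duration is a natural question for this product, so a reader of the interim may well look there.

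**Working it through.** **Inputs from the documents.** Four cohorts of about 16, and 4 × 16 = 64, which matches the stated total. SAP 3.1.1 says the size does not come from a power calculation, so there is no further figure to reproduce. The interim is 8 weeks after the last treatment, each gate is at least 4 weeks after the last treatment of the stage before, and visits are at Weeks 2, 4, 8, 12, 16, 20 and so on to 36.

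**Assumptions, not in the documents.** Each stage enrols evenly over E weeks. G weeks pass between the Week 4 gate and the next cohort's first treatment. The true responder rate is 60% in every cohort at the visit shown.

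**Minimum follow-up at the cut, from the documents alone**
- Cohort 4: 8 weeks.
- Cohort 3: 8 + 4 = 12 weeks.
- Cohorts 1 and 2: 8 + 4 + 4 = 16 weeks.

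Visits through Week 8 are therefore due for everyone. Week 12 is due for all of Cohorts 1 to 3 but not for all of Cohort 4.

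**Range of follow-up once enrolment time is included**
- Cohort 4: 8 to 8 + E.
- Cohort 3: 12 + E + G to 12 + 2E + G.
- Cohorts 1 and 2: 16 + 2E + 2G to 16 + 3E + 2G.

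Share due at visit v = (longest follow-up − v) / E, held between 0 and 1. For Cohort 4 this is (E − 4)/E at Week 12 and (E − 8)/E at Week 16. Displayed rate = true rate × share due.

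| E (weeks) | Cohort 4 due, Week 12 | Shown for a true 60% | Cohort 4 due, Week 16 | Shown for a true 60% |
|---|---|---|---|---|
| 4 | 0/4 = 0% | 0% | 0% | 0% |
| 8 | 4/8 = 50% | 30% | 0/8 = 0% | 0% |
| 12 | 8/12 = 67% | 40% | 4/12 = 33% | 20% |

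Placing 16 subjects at equal intervals from the first to the last day of the stage gives nearly the same picture: 1, 8 and 11 of 16 due at Week 12.

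**Cohort 3.** Its shortest follow-up is 12 + E + G, so it is complete at Week 12 in every scenario. It falls short at Week 16 only if E + G is below 4. With E = 2 and G = 0, follow-up runs from 14 to 16 weeks and 1 of 16 is due. With E = 4 and G = 2, follow-up runs from 18 to 22 weeks: Week 16 is complete, and at Week 20 the share due is (22 − 20)/4 = 50%. Week 20 would then show 60% in Cohorts 1 and 2 (follow-up 28 to 32 weeks), 30% in Cohort 3 and 0% in Cohort 4, with no true difference.

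**What the intervals would show.** The exact 95% interval for 0/16 is 0% to 20.6%, which looks informative although no one has been observed. For 8/16 it is 24.7% to 75.3%. As an illustration, 8, 8, 8 and 0 responders of 16 (a true 50% throughout, no one in Cohort 4 due) give an asymptotic Cochran-Armitage z = −12/√18.75 = −2.77, p = 0.006. The SAP names a trend test for Week 4 only, so this shows the size of the artefact and is not a planned analysis.

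**The case against.** The strongest reply is that the artefact may never appear. SAP 3.4.2 describes a high-level analysis limited to asterisked items and focused on primary and secondary endpoints. The primary endpoint is at Week 4. The one persistence endpoint that can be read, time to return to baseline in SAP 6.5.3.2, is exploratory and summarised by Kaplan-Meier. An interim set at 8 weeks also suggests a readout through Week 8, and a redacted part of the SAP may hold an exception. This stands as a condition on the point: if no interim proportion goes past Week 8, nothing changes. It does not remove the point, because SAP 6.5 as written covers all visits and does not stop at Week 8.

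It is also fair that little hangs on this interim. All subjects have been treated, the DRC gates use Week 4 data, Protocol 9.4 plans no formal tests, and an open-label study team knows the enrolment dates. That lowers the priority. A table of percentages and exact intervals can still travel beyond the people who know those dates.

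A reader might infer that the effect would appear to vanish in both later cohorts. The arithmetic does not support that: Cohort 3 is complete at Week 12, and Cohort 4 drops to about zero at Week 12 only if enrolment is fast. A reader might also call the safety rule, "By visit safety summaries will use denominators based on the number of subjects with valid observations at that visit", an inconsistency. Observed-case denominators for safety beside population denominators for efficacy are a common and deliberate pairing, and nothing here rests on it.

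**Conclusion.** The point holds as a conditional one. As written, the rule counts subjects not yet due as non-responders in any interim by-visit proportion after Week 8. The effect is mainly on Cohort 4 from Week 12, where 0% to 67% of subjects would be due if the stage enrols over 4 to 12 weeks. The displayed rate would then be 33% to 100% too low in relative terms. Cohort 3 is affected at Week 16 only with very fast enrolment, otherwise at Week 20 or later. The minimum follow-up of 16, 12 and 8 weeks comes from the documents; enrolment times, gate delays and the true rate are assumptions.

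The consequence is a possible false dose-duration pattern at the interim. The documents do not support a wider reading in which the primary result, dose escalation or the final analysis is biased. Week 4 and Week 8 are due for everyone at the cut, the DRC decisions come earlier and rest on Week 4 data, and at the final analysis no visit is still to come. The change is worth making because it costs almost nothing, but it is not critical.

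**What to change.** Add one rule to SAP 3.4.2, with a cross-reference in 6.5:

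> At the interim, by-visit proportions are shown only through Week 8, the last visit that all subjects could have reached. If a later visit is shown, its denominator is the LCL-Evaluable subjects whose scheduled visit date is on or before the data cut or who have already attended that visit, plus those who left the study earlier and would have been due by the cut. The number due is displayed for each cohort.

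Using the scheduled date or actual attendance, rather than a closed visit window, matters because Protocol Table 3 allows ±4 days. A closed-window rule would discard subjects who already have data. Keeping early leavers in the denominator preserves the intent of SAP 6.5 for truly missing visits. The population-count denominator stays for the final analysis.

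The cost is a few sentences and one filter in the interim programs. The drawback is that late-visit interim results are either left out or rest on few Cohort 4 subjects with wide intervals, which is a fair picture of the data at that date. If the asterisked tables already end at Week 8, the added text simply records that.

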This is a phase 2a, multicenter, open-label, dose-escalation study to evaluate the safety and efficacy of DAXI for injection for the treatment of subjects with moderate to severe LCL. This study will be conducted at 4 sites in the United States.

Approximately 64 subjects (18 to 65 years old) with moderate to severe LCL will be enrolled sequentially into 1 of 4 treatment cohorts (approximately 16 subjects per cohort) [REDACTED]

[REDACTED] Investigators will make all reasonable efforts to enroll equal proportions of subjects with moderate and severe LCL (based on baseline assessments) in each dosing cohort.

The total study duration will be up to 38 weeks, including up to 2 weeks for screening. Subjects will be followed for a minimum of 24 weeks from LCL treatment and up to 36 weeks or until scores on the maximal expression IGA-LCWS and PLCWS return to baseline, whichever occurs first. Subjects will then have a Final Evaluation Visit. Baseline, unless otherwise stated, refers to the last available assessment prior to LCL treatment (Day 1 Visit).

All treatments will be IM injections administered by the principal investigator (PI). [REDACTED]

[REDACTED]

[REDACTED]

[REDACTED]
 
[REDACTED]
 
[REDACTED]
 
[REDACTED]
 
[REDACTED] Revance has this right to stop or terminate the study at any time for any reason at their discretion or in consultation with the DRC.

Study Visits:
 
Study visits will occur at the Screening Visit (Day -14), Treatment Visit (Day 1), a safety follow-up phone call at Week 1, and follow-up visits at Weeks 2, 4, 8, 12, 16, 20, 24, 28, 32, and 36. Baseline for all efficacy assessments, unless otherwise noted, will be the last available assessment prior to LCL treatment (Day 1 Visit).

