4.4. Visit Schedule

A Screening Visit will be conducted up to 2 weeks prior to enrollment, and subjects will receive investigational product at baseline (Day 1). Following treatment, subjects will complete a paper diary for 2 weeks to capture their assessment of improvement in the appearance of LCL. A follow-up safety phone call will be conducted at Week 1. Post-treatment on-site follow-up visits

will occur at Weeks 2, 4, 8, 12, 16, 20, 24, 28, 32, and 36. The total study duration will be up to 38 weeks, including up to a 2-week screening period. Subjects will be followed for a minimum of 24 weeks post-treatment and up to 36 weeks or until scores return to baseline for the maximal expression IGA-LCWS and PLCWS or until the Week 36 Visit, whichever occurs first. Subjects will then have a Final Evaluation Visit.

Subjects will be evaluated for LCL severity using the Revance-validated 4-point IGA-LCWS and PLCWS at rest and at maximum smile effort.

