9.4. Statistical Analyses

The statistical analysis plan will be developed and finalized before database lock and will describe the detailed methods of analysis, the subject populations to be included in the analyses, and procedures for accounting for missing, unused, and spurious data. This section is a summary of the planned statistical analyses of the primary and secondary endpoints.

In general, descriptive summaries will include means, standard deviations, and range for continuous variables, and counts and proportions for categorical measures. Unless otherwise

stated otherwise, a 95% confidence interval will be provided for means and proportions. No formal hypothesis tests are planned, but group comparisons may be performed as exploratory analyses. No multiplicity adjustments or imputation of missing data are planned.

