6.5.3.3 Proportions in a Given Category

Changes from baseline in LCL severity will be categorically summarized using number and percentages by summary cohort by visit. Separate summaries will be performed for the IGA-LCWS and the PLCWS.

Subject diary of PLCWS to assess the onset of response (decrease from baseline of at least 1 point) will be summarized categorically.

Responses to the Subject Global Satisfaction with Treatment and FASE questionnaire (subject's perception of how old they think they look following the treatment) at all timepoints after LCL treatment, will be categorically summarized by proportion of subjects with a given response.

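### Subjects who leave from Week 24 because they are back at baseline vanish from the 'no change' rows and from observed-case means at Weeks 28–36 (SAP 6.5, 6.5.3.3)

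*SAP*

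**What the plan says.** **Exit rule.** The Protocol synopsis (Overall Design) states: "Subjects will be followed for a minimum of 24 weeks from LCL treatment". Follow-up then continues "up to 36 weeks or until scores on the maximal expression IGA-LCWS and PLCWS return to baseline, whichever occurs first". SAP 3.1 has the same rule without the words that restrict it to maximal expression: "until scores on the IGA-LCWS and PLCWS return to baseline (Day 1 Visit) or until Week 36, whichever occurs first". On-site visits "will occur at Weeks 2, 4, 8, 12, 16, 20, 24, 28, 32, and 36" (Protocol 4.4), so Weeks 28, 32 and 36 fall after the earliest planned exit.

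**Analysis rules.** SAP 6.5 calls for descriptive summaries of every efficacy measure at each visit, by cohort. It fixes the denominator: "All analyses displaying proportions will use population counts as denominators at all visits regardless of the number of actual observations recorded". SAP 6.5.3.3 adds: "Changes from baseline in LCL severity will be categorically summarized using number and percentages by summary cohort by visit", separately for the two severity scales. SAP 6.5.3.4 summarises FASE and FACE-Q descriptively. Protocol 9.4 says: "No multiplicity adjustments or imputation of missing data are planned".

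**What is not visible.** No readable text separates a planned exit after return to baseline from a missed visit or a dropout, or says how such a subject appears in tables for later visits.

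**The concern.** Attendance at Weeks 28–36 depends on the outcome itself. Those still attending are mainly subjects whose effect persists on at least one scale. Those who have left did so with a known result: both maximum-smile scores at baseline or worse.

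Two things follow if the plan is applied as written. In the change-category tables, a leaver counts in the denominator but in no row, so the unfavourable row is too small and the rows do not add to 100%. Any mean taken over observed values describes only subjects still in follow-up. The quoted denominator sentence causes the first effect. The second comes from observed-case summaries combined with the absence of imputation.

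At stake is the late-visit description of durability in cohorts of about 16. The change tables could look more favourable than the Kaplan-Meier results in the same report.

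**Working it through.** The plan states no figure to reproduce here. The check is arithmetic on one cohort.

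**Inputs from the documents**
- Cohort size N of about 16 (Protocol 4.1).
- Earliest planned exit at Week 24; later visits at Weeks 28, 32 and 36.
- Leavers have change 0 (or worse) on both maximum-smile scales, by the exit rule.

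**Assumptions**
- The exited fraction f is not given. I use 25%, 50% and 75% (4, 8 and 12 of 16).
- Attenders have a mean change of −1.0, and a quarter of them are at no change on the scale tabulated.
- Leavers stay at baseline after exit, and there is no other missing data.

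**Formulas.** Let *e* be the number exited (f = e/N), *a* the number of attenders at no change or worse, and *m* the mean change among attenders.
- Category as planned: a/N. With leavers counted: (a + e)/N. The difference is e/N = f.
- Sum of the rows as planned: (N − e)/N = 1 − f.
- Cohort mean with leavers at 0: (1 − f)·m. The observed mean m is therefore 1/(1 − f) times the cohort mean.

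| Exited | 'No change' as planned | With leavers counted | Rows sum to | Mean as planned | Cohort mean | Ratio | Improved, either way |
|---|---|---|---|---|---|---|---|
| 4 of 16 | 3/16 = 18.8% | 7/16 = 43.8% | 75% | −1.00 | −0.75 | 1.33 | 9/16 |
| 8 of 16 | 2/16 = 12.5% | 10/16 = 62.5% | 50% | −1.00 | −0.50 | 2 | 6/16 |
| 12 of 16 | 1/16 = 6.3% | 13/16 = 81.3% | 25% | −1.00 | −0.25 | 4 | 3/16 |

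For the middle row the exact 95% intervals are 1.6–38.3% as planned and 35.4–84.8% with leavers counted.

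**Does the both-scales rule remove the problem?** An attender can be at no change on one scale while the other still shows benefit. A simulation with correlated log-normal return times on the two scales (log-scale SD 0.35, one-grade effect) allowed for this. With an assumed median of 24 weeks and correlation 0.8:
- Week 28: 60% still attending; mean change −0.55 observed against −0.33 for the cohort; 'no change' 27% against 67%.
- Week 36: 28% still attending; −0.44 against −0.12; 15% against 88%.
- Improved proportion over the full cohort: 33% against 33% at Week 28, and 12% against 12% at Week 36.

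With assumed medians of 20 to 28 weeks and correlations of 0.5 and 0.8, the share gone before Week 28 ran from 18% to 61%. The direction was the same throughout.

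**Scope.** The factor 1/(1 − f) applies only where leavers are known to sit at zero change, that is, to maximum-smile IGA-LCWS and PLCWS. Nothing puts leavers at zero on FACE-Q, FASE, satisfaction or the at-rest scores.

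**The case against.** **Durability is analysed elsewhere.** Protocol 9.4.1 assigns duration to time-to-event endpoints. SAP 6.5.3.2 gives Kaplan-Meier estimates of return to baseline on both scales, where the exit is the event. This stands: that analysis is sound, and the problem is confined to the by-visit tables beside it.

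**The fixed denominator is conservative.** This is true for responder proportions, since a subject back at moderate or severe is a non-responder. Moving to observed denominators would be wrong: with 8 exited it would turn 6/16 (37.5%) into 6/8 (75%). The objection does not cover unfavourable categories, where the same rule works in the favourable direction.

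**The mean may never be tabulated.** The visible SAP specifies a mean severity change only at Week 4 (6.5.1). A late one is implied only by the general sentence in 6.5. This stands, so the multiplier applies if such a mean is produced.

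**A rule may be redacted, or sit in the shells.** Parts of SAP sections 5 and 6.5 are blacked out, and the table shells are a separate document. An early-completer row or visit-mapping rule could be there. Protocol 9.4 plans no imputation, which makes a carry-forward less likely but says nothing about row labels. This limits confidence.

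**Stronger readings that the documents do not support.** A reader might infer that late tables in general would show a persisting effect, but responder rows decline correctly. A reader might infer that dissatisfaction is understated, but leavers' later satisfaction is unknown. A reader might infer that the distortion differs by dose, but no document says that exit rates do.

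**Conclusion.** The point holds on the visible text. At Weeks 28–36, 'no change or worse' on the two maximum-smile severity scales is understated by exactly the fraction that has exited under the return-to-baseline rule, and the rows fall short of 100% by the same amount. A mean maximum-smile change, if tabulated, overstates improvement by 1/(1 − f). Late means of FACE-Q and FASE describe only subjects still in follow-up, by an unknown margin.

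The sizes rest on assumed exit fractions and on leavers remaining at baseline. Larger multiples can be obtained by assuming a return-time distribution, but the documents give none. Protocol section 2 puts the usual duration of type A toxin at 4 to 5 months (about 17–22 weeks). That makes appreciable exit from Week 24 plausible but does not quantify it for this product.

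The Week 4 primary endpoint and model, population-denominator responder proportions and the Kaplan-Meier analysis are not affected. In an open-label phase 2a study without formal testing, severity is moderate and confidence is limited by the redactions.

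**What to change.** In SAP 6.5 and 6.5.3.3, unless a redacted rule already does this:

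- **(a)** Count subjects who exit under the return-to-baseline rule as returned to baseline (change 0 or worse, as observed at exit) at later scheduled visits. Do so in the maximum-smile IGA-LCWS and PLCWS category tables and in any mean. At the least, add a row such as 'completed early – returned to baseline', which avoids any conflict with the Protocol's statement on imputation. Show true dropouts separately.
- **(b)** Give the observed n and label Week 28–36 summaries of at-rest scores, FACE-Q, FASE and satisfaction, and any GAIS means, as 'subjects still in follow-up'. Keep population denominators for responder proportions, including GAIS.
- **(c)** Show Final Evaluation data at the actual visit week. Protocol 8.2.5 ties that visit to Week 36 in its title; pooling early final visits there would make leavers disappear at Weeks 28 and 32 and reappear at Week 36.

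The exit wording in SAP 3.1 should also be reconciled with the Protocol, so that the derivation refers to one rule.

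The cost is a small derivation and some table labels, with no new data. Late-visit figures become less favourable.
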